1. * Describe who will be recruiting individuals for participation for this study:

The study team will be responsible for recruiting individuals for participation in this study.

2. * Select all methods to be used for recruitment:

Flyers/Posters or Brochures Pitt+Me Other

* Enter description of 'Other' method of recruiting:

Individuals will be recruited into this study through word of mouth. Potential subjects recruited through word of mouth will be provided both an email address and phone number to contact for study enrollment.

Study flyers will be posted around the University of Pittsburgh's campus. The study flyers will be used to provide general information about the study and contact information for potential participants to get in contact with the study team.

3. * Provide details on your recruitment methods:

Individuals from local colleges will be approached for recruitment into the study, including the University of Pittsburgh School of Medicine, University of Pittsburgh, and Duquesne University. These individuals will be recruited using word of mouth, as detailed in the above response. Individuals will also be recruited through word-of-mouth and Pitt+Me.

Students will not be required to participate in the research study and individual students will not be specifically targeted. Potential participants will be solicited from a "broad base" of individuals meeting the conditions for the study.

4. * Describe all compensation/incentives offered to participants and timing of these offers:

Patients will be compensated \$300 after completion of three visits. Payment will be given on a reloadable Vincent debit card. The payment will not be separated by visit but will instead be provided pending successful completion of the three study visits.

5. Recruitment materials: (attach all material to be seen or heard by subjects, including advertisements and scripts)

Doc	ument	Category	Date Modified	Document History
View Rec Flye	y ruitment er(2)	Recruitment Materials	7/6/2023	History

Study Aims

* Describe the purpose, specific aims, or objectives and state the hypotheses to be tested:

The study aims include:

1. Evaluate if giving BUOY will decrease the total volume of urine excretion

2. Determine is BUOY will lead to bigger increase in Total Body Fluid

3. Determine if there are quantifiable differences between giving BUOY in divided doses versus a bolus of NUUN

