- Total number of subjects to be enrolled at this site (enter -1 for chart reviews, banking, registries):
 34
- 2. Describe and explain the study design:

The proposed study will be conducted as a single-center prospective, cross-over, placebo-controlled clinical trial at the University of Pittsburgh Medical Center (UPMC).

3. Describe the primary and secondary study endpoints:

Urine volume (collected each visit over 6-hour time frame) Electrolytes: sodium, potassium, chloride Urine osmolarity Urine creatinine

4. Provide a description of the following study timelines:

Duration of an individual subject's active participation:

The individual's active participation will involve three separate sessions, each lasting approximately 6 hours (total of 18 hours for each participant). Study visits will be completed within a three-to-four month period.

Duration anticipated to enroll all subjects:

Approximately 9 months

Estimated date for the investigator to complete this study (complete primary analyses):

4/1/2024

5. List the inclusion criteria:

- Male or female, >18 to 45 years of age
- Freely given written consent
- Non-tobacco users
- Negative pregnancy test in women of childbearing potential
- BMI < 35 kg/m2
- GFR > 60 ml/min
- No known underlying medical condition
- Willing to refrain from EtOH for 24h prior to test day
- Willing to refrain from strenuous exercise for 24 h prior to each test day
- Acceptable to have one 8oz cup of coffee/liquid on the morning of the test, but must be consistent each visit
- · Without active infection of any kind
- Engaged in exercise three or more hours per week

6. List the exclusion criteria:

- Abnormal creatinine (Cr > 1.2).
- Proteinuria / hematuria / glucosuria based on urine dipstick.
- Diagnosed medical condition that would impede results (CHF, HTN, CAD, CKD,
- history of electrolyte abnormality).
- Pregnancy
- Use of diuretics within past 2 weeks
- Obesity (BMI > 35)
- Active infection based on symptoms (bacterial or viral)

• Hemodynamic abnormality at screening visit: Blood pressure less than 100/60 or greater than 140/90.

7. Will children or any gender, racial or ethnic subgroups be explicitly excluded from participation?

• Yes O No

* Identify the subgroups and provide a justification:

Children will be excluded from participation since the study is looking at the hydration status of active adults.

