8. Describe the power analysis used and cite your method of statistical analysis. If a power analysis is not possible, thoroughly justify the sample size required for the study, including appropriate literature citation (alternatively provide page reference in attached protocol):

The data will be presented as mean \pm SD, analyzed using the conditions x time analysis of variance (ANOVA), while BHI will be analyzed using a one-way ANOVA. Tukey post-hoc testing and contrast analysis can be used as appropriate. Statistical significance was set at p \leq 0.05.

We aim to have 30 subjects complete the study. This is a pilot study to inform a future large-scale trial with appropriate power calculation.

Research Activities

 * Provide a detailed description of all research activities (including screening and follow-up procedures) that will be performed for the purpose of this research study. This description of activities should be complete and of sufficient detail to permit an assessment of associated risks.

Prior to initiation of the study, subjects will complete a brief phone screen to assess basic eligibility and will be asked to fast. The screening visit will consist of informed consent, health history, and discussing eligibility requirements for each study visit, including (1) refrain from vigorous exercise for 24 hrs prior, (2) fast overnight for at least 10 hrs, (3) empty bowel and bladder upon waking up, (4) can consume one 8oz cup of coffee or tea. For female subjects, this will also include their last date for menstruation and/or birth control method to take into consideration the effects of ovulation on water retention.

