Prior to all research visits (screening, visits 1, 2, and 3), participants must refrain from vigorous exercise (exercises that results in a high heart rate and rapid breathing) within 24 hours of study visit. Participants will fast (food) overnight for 10h prior to initiation of test. Upon waking they are asked to empty their bowel and bladder. They can consume one 8oz cup of coffee or tea (plain with no sugar or additives) to reduce caffeine headaches. They will present at 7-8am, which will be pre-specified. Prior to emptying their bladder, a blood draw of up to 1 ml will be drawn by a trained phlebotomist for the i-STAT testing, which will be used to measure creatine and electrolytes. After this they will be asked to empty their bladder. Immediately after emptying the bladder, bioimpedence will be measured. Females will be administered a urine pregnancy test. A urinalysis dipstick for protein/blood/glucose and i-STAT measurement for creatinine and electrolytes will be completed to confirm eligibility. Next, the subject will be asked to rest for 5 mins, after which baseline vitals will be taken, including blood pressure, heart rate, weight. For Visit 2 and Visit 3, the participant will be asked to review medical history and any change in status may warrant an additional baseline creatinine and blood/protein test to confirm eligibility. All studies will be repeated in the same subject using either Buoy (intervention) or water (control) or Nuun (intervention). Urine will be collected at four specific timepoints during the intervention and the volume will be recorded. If participants need to urinate between scheduled collection times, urine will be collected, volume recorded, and combined with the urine collection of the following timepoint. These urine samples will be measured and a fraction of it will be sent to the lab to be tested for the following electrolytes: sodium, potassium, chloride and urine osmolarity. Urine creatinine will also be tested at these timepoints. Additional food or beverage will not be allowed throughout the study period.

VISIT 1---BUOY INTERVENTION: The goal is to give 600mg of Na+ over 4 hours while measuring urine output over 6 hours. The recommended Buoy dosage is ¹/₃ tsp in 237 ml of water (50mg Na+) multiple times a day (Table 1). Therefore, to safely achieve a total dose 600mg Na+ (6-fold increase from single dose) we will use 4 tsps (18 ml) of Buoy diluted in 1 L of water.

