Prior to initiation of test blood pressure and heart rate will be measured. Urine will be collected and discarded.

At time 0, the participant will begin to drink fluid (drinking 6.25% of their total amount every 15 min). Urine will be collected at 60, 120, 240, and 360 min. Bioimpedence will be measured after each urine collection. Collect urine for a total of 6 hours. VISIT 2—WATER CONTROL: Participants will ingest 1 L of water at a rate of 6.25% of the calculated amount of water every 15 min for 4 hours.

Prior to initiation of test blood pressure and heart rate will be measured. Urine will be collected and discarded.

At time 0, the participant will begin to drink fluid (drinking 6.25% of their total calculated amount every 15 min). Urine will be collected at 60, 120, 240, and 360 min. Bioimpedence will be measured after each urine collection. Collect urine for a total of 6 hours.

VISIT 3—NUUN INTERVENTION: The goal is to give a one-time dose of 2 tablets of Nuun Sport (600mg Na+) at the start of the trial, diluted in 1L water to be consumed within 30 min (similar to prior published data, Pence 2020).

Prior to initiation of test blood pressure and heart rate will be measured. Urine will be collected and discarded.

At time 0, the participant will consume the beverage over 30 min. Urine will be collected at 60, 120, 240, and 360. Bioimpedence will be measured after each urine collection. Collect urine for a total of 6 hours. Patients will be compensated \$300 after completion of three visits.

Buoy is an all-natural, organic, FDA compliant dietary electrolyte supplement that can be dissolved in 8-12oz water (or other liquid) and provide electrolytes in servings of 1/3 teaspoon. Nuun are electrolyte tablets that are added to water to improve fluid balance and beverage hydration index (BHI) in healthy individuals (Pence, 2020). Nuun tablets contain a mix of electrolytes, including calcium, magnesium (as an oxide), chloride, sodium, and potassium. The recommended use of Nuun is one tablet dissolved in water, administered once daily.

The PI and study team will be performing the research procedures. A phlebotomist will be used to complete the blood draws.

Following each study visit, a boxed lunch will be offered to each participant. This lunch will be Jimmy John's (or a similar sandwich shop). Each participant will be asked about preferences and food allergies during the screening process so provide an appropriate option for participants involved.

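### Neither planned ANOVA names a participant or repeated-measures term, although every participant takes all three beverages; run as written, the error terms ignore the pairing

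*Combined protocol and SAP*

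**What the plan says.** Study Design item 2 describes a single-centre cross-over. Research Activities item 1 confirms that each person supplies every condition: "All studies will be repeated in the same subject using either Buoy (intervention) or water (control) or Nuun (intervention"). Within each visit, "Urine will be collected at 60, 120, 240, and 360 min", so a participant who completes the trial gives 3 × 4 = 12 serial values per urine outcome.

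The analysis is set out in one short paragraph, Study Design item 8. The data are to be "analyzed using the conditions x time analysis of variance (ANOVA), while BHI will be analyzed using a one-way ANOVA". It adds that "Tukey post-hoc testing and contrast analysis can be used as appropriate", sets significance at p ≤ 0.05, aims for 30 completers, and gives the purpose: "This is a pilot study to inform a future large-scale trial with appropriate power calculation".

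Nothing in the document mentions a paired, within-subject, mixed or random-participant term, a covariance structure or a sphericity correction. Aim 1 is to "Evaluate if giving BUOY will decrease the total volume of urine excretion", and Study Design item 3 lists "Urine volume (collected each visit over 6-hour time frame") among the endpoints. BHI is spelled out in Research Activities ("improve fluid balance and beverage hydration index (BHI) in healthy individuals"), but no formula is given.

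**The concern.** A cross-over is chosen so that each participant serves as his or her own control. That gain is realised only if participant is in the model. As ordinarily understood, a one-way ANOVA compares independent groups. Applied to three values from the same person, it puts the between-person variance into the error term, and Tukey tests built on it inherit the same error. A factorial conditions-by-time ANOVA without a participant term has a second fault: it counts four collections from one visit as four independent replicates of the beverage effect.

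Two things are at stake. The nominal 5% may not be the real error rate, and the direction differs between tests. The pilot is also meant to feed a later power calculation. If that trial is again a cross-over, it needs the SD of within-person differences, which neither the mean ± SD per beverage nor an unpaired ANOVA reports.

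**Working it through.** **Inputs.** From the documents: 3 beverages, 4 collections per visit, 30 completers, α = 0.05. The documents give no SD, correlation or effect size, so there is no planned figure to reproduce. Everything below is in units of the total SD and rests on stated assumptions.

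**1. One value per visit (one-way test).** Model: participant effect with variance ρ plus error with variance 1 − ρ, and equal variances. With no beverage effect, the between-beverage mean square has expectation 1 − ρ, but the literal error mean square has expectation 1. The F ratio is therefore too small whenever ρ > 0. Error degrees of freedom are 3 × 30 − 3 = 87 as written and 2 × 29 = 58 with participant.

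For a 0.5 SD shift in one beverage, the effects (0, 0, 0.5) have sum of squares about their mean 0.25 − 3 × (1/6)² = 1/6. The noncentrality with participant is then 30 × (1/6)/(1 − ρ) = 5/(1 − ρ). The 95% CI half-width of a pairwise difference is 1.988 × √(2/30) = 0.513 as written and 2.002 × √(2(1 − ρ)/30) with participant.

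| | ρ = 0.3 | ρ = 0.5 | ρ = 0.7 |
|---|---|---|---|
| Size of the 5% test, as written | 1.5% | 0.4% | 0.02% |
| Power, as written | 46% | 43% | 39% |
| Power, participant in model | 64% | 79% | 95% |
| Tukey power vs water, as written | 30% | 28% | 24% |
| Tukey power vs water, participant in model | 47% | 63% | 87% |
| CI half-width, as written | 0.51 | 0.51 | 0.51 |
| CI half-width, participant in model | 0.43 | 0.37 | 0.28 |

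The as-written size and power come from 400,000 simulated trials per ρ and the Tukey powers from 200,000. The power with participant is exact from the noncentral F(2, 58).

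**2. Conditions by time.** Split the total variance of 1 into person, visit (participant-by-visit) and residual shares, with independent, equal-variance residuals. The literal error has 12 × 30 − 12 = 348 df and expectation 1. With no effect, the condition mean square has expectation residual + 4 × visit, and the interaction mean square has expectation residual. The condition test is too strict when the first quantity is below 1 and too liberal when it is above 1.

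| Person / visit / residual | Residual + 4 × visit | Size of condition test |
|---|---|---|
| 0.5 / 0 / 0.5 | 0.5 | about 0.3% |
| 0.5 / 0.1 / 0.4 | 0.8 | 2.7% |
| 0.3 / 0.1 / 0.6 | 1.0 | 5% |
| 0.3 / 0.2 / 0.5 | 1.3 | 10% |
| 0.3 / 0.3 / 0.4 | 1.6 | 15% |
| 0.2 / 0.3 / 0.5 | 1.7 | 17% |

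The condition-by-time test has size of at most 0.3% in all six rows, and 2.9% at 0.1 / 0 / 0.9.

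**3. Condition-by-time under other covariances.** The collection intervals last 60, 60, 120 and 120 min, so equal variances cannot be assumed. With visit share 0 and within-visit residual correlation −0.2, the size is 7.0% at person share 0.1 and 4.3% at 0.2. If the two longer intervals also have twice the SD, it is 8.0%, 5.3%, 3.1% and 0.6% at person shares 0.1, 0.2, 0.3 and 0.5. With independent residuals, one interval at three times the SD and person share 0.1, it is 7.0%.

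With participant in the model, the condition test on visit means held 4.8% to 5.2% in all 15 scenarios run. The uncorrected condition-by-time test held 4.8% to 5.0% with equal variances but 6.2% to 9.4% with unequal ones. With a Greenhouse-Geisser correction it was 3.6% to 4.7%.

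**4. Pilot purpose.** The SD of a paired difference is √(2(1 − ρ)) = 1.18, 1.00 or 0.77 at ρ = 0.3, 0.5 or 0.7. For a 0.5 SD shift at 80% power and two-sided 5%, a two-beverage cross-over needs 46, 34 or 21 participants. The SD per beverage is 1 in all three cases, so it cannot tell them apart.

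**The case against.** The strongest reply is that the paragraph is incomplete rather than wrong. In a trial described as a cross-over, conditions-by-time ANOVA is a common shorthand for a within-subject analysis. That is a fair possibility, but the text does not say so. The reading does not extend easily to a one-way ANOVA, nor does it supply an error term for the Tukey tests.

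Other points limit the size of the concern:

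- Item 8 assigns the one-way test only to BHI, which is not in the endpoint list. If BHI is scaled to the participant's own water visit, water is a constant and the three-group, equal-variance figures in step 1 would not describe it. This stands.
- Size above 5% for condition-by-time is a corner case. It needs small person variance, no visit variance, and either negative within-visit correlation or one very variable interval. With independent residuals and SDs of 1:1:2:2 at person share 0.1, the size is about 4.4%. In the negative-correlation cases the condition test is very strict, so the two kinds of inflation do not arise together there. This also stands.
- All variance shares are assumed. This is true, and the spread from 0.3% to 17% shows that the error rate is uncontrolled, not that it has a particular value.
- The participant-level data will exist, so paired SDs could be computed later. This is true; what the plan lacks is a commitment to report them.
- A pilot need not be powered. This is agreed, and no power claim is disputed here. The pilot label does not excuse an error structure that does not match the design.

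**Conclusion.** The concern holds. The plan states an independent-groups method for BHI and an unspecified error structure for the serial outcomes, in a design where every observation is paired.

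On the literal reading, with positive between-visit correlation and equal variances, the one-way test and its Tukey comparisons are conservative. At correlation 0.5 the pairwise interval is 0.51 SD wide on each side where 0.37 SD was attainable. For the conditions-by-time ANOVA, no single direction can be claimed: the condition test may be too strict, about right or too liberal, and the condition-by-time test is usually far too strict. These sizes depend on the assumed variances and on 30 completers. The mismatch between design and analysis does not. It should be fixed before analysis.

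**What to change.** In Study Design item 8:

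- State a repeated-measures ANOVA or linear mixed model with participant as a random effect and beverage as a fixed effect.
- For serial outcomes, add time, beverage-by-time, and a participant-by-visit effect or within-visit covariance. For the beverage-by-time test, name an unstructured within-visit covariance or a Greenhouse-Geisser correction, since the participant term alone does not protect that test when interval variances differ.
- Analyse cumulative 6-hour urine volume (aim 1) and BHI with one value per visit.
- Take the Tukey tests and contrasts from the same model, with 95% CIs for within-person differences.
- Report the SD of paired differences for the future power calculation.
- Say how BHI is computed. If it is relative to the participant's own water visit, do not enter the constant water value as a group.

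The cost is a rewording of one paragraph plus one line on BHI, with no new data and no design change. A participant term will not separate beverage from visit order, which Research Activities appears to fix (Buoy at Visit 1, water at Visit 2, Nuun at Visit 3). That is a separate issue.

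### Aim 2 asks about an increase in body fluid, but the plan lists no body-fluid endpoint, names no Buoy-water contrast and gives the pre-dose bioimpedance reading no role (minor; fixable by wording)

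*Combined protocol and SAP*

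**What the plan says.** - **Aim.** Study Aims, aim 2: "Determine is BUOY will lead to bigger increase in Total Body Fluid".
- **Endpoints.** Study Design, item 3, in full: "Urine volume (collected each visit over 6-hour time frame) Electrolytes: sodium, potassium, chloride Urine osmolarity Urine creatinine". Primary and secondary are not distinguished, and neither body fluid nor bioimpedance appears.
- **Readings.** Research Activities, item 1, in the general pre-test paragraph: "Immediately after emptying the bladder, bioimpedence will be measured". The description of each of the three visits adds: "Bioimpedence will be measured after each urine collection", with collections at 60, 120, 240 and 360 minutes. No section states that bioimpedance is the measure of total body fluid, though nothing else planned could serve.
- **Analysis.** Study Design, item 8: data are "analyzed using the conditions x time analysis of variance (ANOVA"), with a separate one-way ANOVA for the beverage hydration index. It adds: "Tukey post-hoc testing and contrast analysis can be used as appropriate". Body fluid is not mentioned.
- **Purpose.** The same item: "This is a pilot study to inform a future large-scale trial with appropriate power calculation". Thirty completers are intended; no SD, effect size or power is given.
- **Order.** Research Activities, item 1 labels Visit 1 Buoy, Visit 2 water and Visit 3 Nuun. No randomised order is described.

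**The concern.** An increase needs a starting value. The plan appears to collect one at each visit but does not say whether it is a level of time, is subtracted, is a covariate or is unused. At least three analyses fit the wording:

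1. Pre-dose reading as a fifth level of time. The condition-by-time interaction then tests differential change, but jointly over three drinks and five times, not for Buoy against water.
2. Pre-dose reading omitted. Post-dose levels are compared, which is not Aim 2's question.
3. A contrast on plain change. This is allowed, but neither named nor tied to a time point.

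The choice can be made after the data are seen, and the options can differ widely in power. The error variance handed on to the future powered trial also depends on it.

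**Working it through.** The plan states no power figure, so there is none to reproduce.

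**From the documents:** 30 completers, three conditions in the same person, one pre-dose and four post-dose readings per visit, significance level 0.05 (taken as two-sided).

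**Assumed, not in the documents:** correlation r between readings of one visit (after removing stable differences between people) of 0.3, 0.5 or 0.8; equal variances, with the SD of one reading set to 1; a Buoy-water shift of 0.5 SD at all four post-dose times; Nuun equal to water.

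**Interaction test.** With the pre-dose reading as a level of time: (3 − 1) × (5 − 1) = 8 df, with error df 8 × 29 = 232.

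**Error variance V of the visit mean of four post-dose readings, constant correlation:**

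| Analysis | Formula | r = 0.3 | r = 0.5 | r = 0.8 |
|---|---|---|---|---|
| Levels alone | (1 + 3r)/4 | 0.475 | 0.625 | 0.850 |
| Plain change | (1 + 3r)/4 + 1 − 2r | 0.875 | 0.625 | 0.250 |
| Pre-dose covariate | (1 + 3r)/4 − r² | 0.385 | 0.375 | 0.210 |

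The covariate variance is lower than levels by r² and lower than plain change by (1 − r)². Neither gap can be negative. The price is one df (58 to 57) and a factor of 57/56 for the estimated slope.

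**Detectable difference at 80% power.** SE = √(2V/30). At r = 0.3 with the covariate, √(2 × 0.385 × (57/56)/30) = 0.162, which gives 0.46 SD. In full, for r = 0.3, 0.5, 0.8:
- covariate 0.46, 0.45, 0.34 SD
- levels 0.51, 0.58, 0.68 SD
- plain change 0.69, 0.58, 0.37 SD

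**Simulated power (%), r = 0.3 / 0.5 / 0.8:**

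| Scenario | Covariate contrast | Levels | Plain change | 8-df interaction |
|---|---|---|---|---|
| Flat 0.5 SD, constant r | 86 / 87 / 99 | 79 / 67 / 55 | 52 / 67 / 97 | 33 / 46 / 90 |
| Flat 0.5 SD, decaying r | 87 / 80 / 83 | 87 / 77 / 58 | 42 / 46 / 70 | 27 / 33 / 60 |
| Building 0.2, 0.4, 0.6, 0.8 SD | 86 / 87 / 99 | – | – | 64 / 81 / 99.8 |
| Late 0, 0.2, 0.6, 1.2 SD | 86 / 86 / 98 | – | – | 99 / 100 / 100 |

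Both building shapes average 0.5 SD: (0.2 + 0.4 + 0.6 + 0.8)/4 and (0 + 0.2 + 0.6 + 1.2)/4. With no effect, all analyses reject about 5% of the time. At r = 0.1 the covariate adds nothing over levels (92% each).

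**Why a late effect is plausible.** Buoy and water are both sipped in equal portions; for water, "6.25% of the calculated amount of water every 15 min for 4 hours". Four portions by 60 minutes is 25%, eight by 120 minutes is 50%, and sixteen by 240 minutes is 100%.

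**Fixed order.** Suppose starting body fluid differs by 0.2 SD between the Buoy and water visits for a lasting reason unrelated to the drink. Levels are off by 0.20 SD. The covariate contrast is off by 0.2 × (1 − r) = 0.14, 0.10, 0.04 SD. Plain change is off by 0. Dividing by the covariate SEs (0.162, 0.160, 0.119), its false-positive rate becomes about 14%, 9% and 6%; plain change stays near 5%.

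**The case against.** The strongest reply is that the planned condition-by-time ANOVA already handles the baseline. With the pre-dose reading as a level of time, its interaction is a valid test of differential change, and a lasting start difference cancels out of it. The plan also allows contrasts, and it is a pilot with no power claim. Much of this stands. A reader might infer that the planned ANOVA cannot address Aim 2; the documents do not support that. What they lack is a statement that the reading is a level of time, and a named Buoy-water comparison.

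A reader might also infer that covariate adjustment is the best or nearly best analysis throughout. It is not. With a late-building effect the interaction is clearly stronger, and a contrast averaged over four times gives full weight to the 60-minute reading, when only a quarter of the drink has been taken.

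Third, with drinks tied to visit numbers, the covariate contrast keeps part of any lasting visit difference that plain change removes, and plain change is the more literal reading of an increase. This stands, and it is why plain change cannot be relegated to a footnote.

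Finally, a pre-dose reading at all three visits is the natural reading of the pre-test paragraph, not a certainty. The visit descriptions do not repeat it. The same paragraph includes a blood draw that Research Activities, item 3 places at screening, with repeats at Visits 2 and 3 only after a change in status.

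**Conclusion.** The gap holds in a limited form. Aim 2 has no listed endpoint, no named contrast and no stated use of the pre-dose reading.

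For a given Buoy-water contrast under constant correlation, using that reading as a covariate gives an error variance no larger than plain change or levels alone, apart from one degree of freedom. The gain ranges from large (86% against 52% for plain change at r = 0.3) to slight (99% against 97% at r = 0.8). Under decaying correlation it is only about 1 and 3 points over levels alone at r = 0.3 and 0.5. The correlation, effect size and effect shape are all assumptions.

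Two stronger conclusions are not supported: that the adjusted contrast is uniformly more powerful than the planned interaction, and that adjustment repairs the fixed visit order. Severity is minor: a free improvement to one analysis in a pilot.

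**What to change.** 1. **Study Design, item 3.** Add total body fluid by bioimpedance, as change from the same-visit pre-dose reading at 60, 120, 240 and 360 minutes.
2. **Research Activities, item 1.** State under each of Visits 1, 2 and 3 that bioimpedance is read before drinking starts.
3. **Study Design, item 8.** Add a paragraph to this effect: *Change in body fluid from the same-visit pre-dose reading will be analysed in a repeated-measures model with participant as a fixed effect, visit within participant as a random effect, condition, time and their interaction, and the same-visit pre-dose reading as a covariate. The Aim 2 test is one Buoy-water contrast at [stated time point, or average of stated times]. The condition-by-time test is retained. The same contrast on change without the covariate is reported with equal prominence, because condition is tied to visit number.*

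Two terms in that model matter. Without the visit effect, treating the four readings of a visit as independent gave simulated false-positive rates of 14%, 19% and 23% at r = 0.3, 0.5 and 0.8. With participant as a random intercept and the raw reading as covariate, the analysis behaved almost like plain change. Assuming a between-person SD five times the within-person SD, its variance relative to levels was 1.42 at r = 0.3, against 1.02 with participant fixed (400 simulated trials, one post-dose reading).

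The team should choose the contrast's time point or average before seeing data, bearing in mind how fast the drink is taken.

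**Cost.** Wording only, with no added participants or visits. If the pre-dose reading was not intended at every visit, one short bioimpedance measurement per visit is added. The fixed visit order is a separate design matter that this change does not resolve.
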